### 1.2.2.2. Safety study endpoint

- 1) The incidence and severity of various adverse events (AE) from the start of oral carbohydrates to the end of the trial;
- 2) The incidence and severity of adverse events such as nausea, vomiting and hypoxemia from the first start of drug administration to the end of the trial;
- 3) Number of antiemetic drugs used within 24h after the first start to drug administration;

## 2. Expected results

Oral carbohydrates in the early postoperative period can improve patient nutritional status, improve comfort and satisfaction without increasing the incidence of adverse events.

## 3. Design and method of the study

### 3.1.1 Screening period

Patients undergoing unilateral total knee arthroplasty of the lower limbs or monocondylar arthroplasty, screened with informed consent to enroll patients, met all enrollment criteria and did not meet any of the exclusion criteria.

### 3.1.2 The perioperative management protocol

Pre-operative management : All patients actively controlled blood pressure, blood glucose, correction of anaemia and hypoproteinaemia, and increased protein intake. The dietary plan was informed by the ward nurse one night before surgery, all patients fasted solid food 6 hours before surgery and 200ml of sugary drinks were taken 2-3 hours before surgery.

Intraoperative management: All patients underwent lumbar anesthesia, selected L3-4 or L2-L3 gap puncture, and the anesthesia plane was controlled below T7. The restrictive liquid management strategy was adopted, 6ml crystalloid · kg · h supplemented physiological requirements, blood loss was supplemented with hydroxyethyl starch fluid, concentrated red blood cells were infused with Hb <80 g / L, and the patient blood pressure and heart rate fluctuation was less than the base value ± 20%. At 30 min before the start of the procedure, 40mg of analgesia at 5mg IV and 2mg of prophylactic antivomiting 30min before the end of the procedure.

Analgesia management:

1. Non-steroidal anti-inflammatory analgesics were given during the operation, and returned to the ward to continue on time;
2. After the operation, the adductor muscle tube block and analgesia should be performed according to the surgical incision site;
3. Sufentanil PCIA analgesia pump, formula: Sufen 150 ug + Segen 6mg + NS250ml; continuous: 3ml / h, control: 5ml, lock: 8min, limit: 35ml / h, adjust the parameters

according to the pain condition to meet the patient NRS pain score 3;

4. If the patient started PCIA treatment, the subject's NRS pain score 4 and 3 bolus did not relieve, and the investigator judged the opioid relief analgesia such as sufentanil or oxycodone until the NRS pain score 3 and recorded;

Management within the PACU:

Eligible patients were screened before surgery, and an informed consent form was signed. Patients enrolled in the experiment were randomly assigned into one of the three groups. They are early feeding group (EOF 1, EOF 2) and late feeding group (control group). Late feeding group (Group C): Group C patients observed 30min vital signs, returned to the ward to fast and drink for at least 6 h, and gradually drink and eat after anal exhaust. Early drinking water group (EOF 1): EOF 1 group received water in the resuscitation room; early drinking carbohydrate group (EOF 2): EOF 2 group received 200ml 12.5% carbohydrate (100ml containing 12.5g maltodextrin, fructose and glucose) in the resuscitation room.

To evaluate the resuscitation room of patients in the early feeding group: Steward awake score of 6 and awake level 3,5ml / kg lean weight 12.5% carbohydrate or water according to the need of consent. The process of drinking carbohydrates or water is to take 30ml orally first. After observing no abnormal swallowing, the patient was instructed to drink the remaining drinks as needed. After the patient returned to the ward, the liquid diet began to gradually excessive into the normal diet. When the patient was able to tolerate a normal diet, the intravenous fluids were stopped.

Evaluation process of drinking index:

1 ) Steward Score: awake: 0-no response to stimulus; 1-some response to stimulus; 2-full awake.(2) Respiratory tract patency: 0-patient's respiratory tract needs support; 1-patient's respiratory tract can maintain patency without support; 2-patient can cough according to the doctor's guidance.(3) Body mobility: 1 point-the patient has no body activity; 2 points-the unconscious activity of the patient's limb; 3 points-the patient's limb can carry out the conscious activities;

2 ) Grade of sobriety: according to the awake degree of the patient's consciousness: Grade 0: the patient is completely in the sleep state, No response when calling; Level Protocol version: May 17, 2023

1: The patient is falling asleep, However, head and neck movement, eye opening, or limb movement occurs during breathing; Grade 2: the patient is awake, Have the same performance as level 1, At the same time can also open the mouth, stretch the tongue; Grade 3: the patient is in an awake state, Have the same performance as the level 2, At the same time, they can also clearly tell their own name, age and other information; Grade 4: The patient is awake, Have the same performance as level 3, It can also accurately identify the surrounding environment, And tell you clearly where you are.3.

3 ) The early feeding group (EOF 1 and EOF2 group) did not need to wait for peristalsis. According to the wishes of the patients, the dose was completed within 2 hours after the operation

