## **1. Study purpose and study endpoint**

### **1.1 Study Purpose**

**1.1.1 Main study objective:** To evaluate the effect of early postoperative oral carbohydrate on postoperative recovery of the unilateral knee arthroplasty.

**1.1.2 Secondary study objectives:** To evaluate the effect of early oral carbohydrate administration on the comfort and safety of patients undergoing unilateral knee arthroplasty.

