## 1.2.2 Secondary study endpoints

### 1.2.2.1 Effectiveness study endpoint

- 1) Fasting insulin resistance index in venous blood was checked on the day of the surgery;
- 2) Fasting insulin resistance index in venous blood was checked 3d after surgery;
- 3) Fasting pre-albumin levels in venous blood on the day of surgery, 1d and 3d after surgery.
- 4) Fasting level of retinol-binding protein in venous blood on the day of surgery, 1d and 3d after surgery;
- 5) The 15-item recovery quality rating scale (QoR-15);
- 6) NRS score of thirst and hunger at 2h, 6h and 8h after surgery;
- 7) Abating distension within 24h after surgery;
- 7) The incidence of hypoxemia and reflux aspiration within 24h after surgery( $SpO_2 <91\%$  under air inhalation was defined as hypoxemia; vomiting associated with severe coughing followed by hypoxemia and lung rales);
- 9) Time of anal exhaust for the first time after surgery;
- 10) The degree of nausea and vomiting;
- 11) Length of hospitalization;
- 12) Postoperative analgesic effect: patients consumed total sufentanil at 48 hours after surgery, number of effective pressure times of the analgesic pump, remediation of analgesia(The salvage analgesic dose was converted to morphine equivalent);
- 13) Postoperative subject satisfaction score.

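### PACU observation time is fixed for Group C only and no common SpO2 or vomiting check times are set, so unequal detection of early safety events cannot be excluded

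*Protocol*

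**What the plan says.** Protocol section 3.1.2, under management within the PACU, describes the early postoperative period separately for each arm.

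- Late feeding: "Group C patients observed 30min vital signs, returned to the ward", followed by at least 6 h of fasting there.
- Early water: "EOF 1 group received water in the resuscitation room".
- Early carbohydrate: "EOF 2 group received 200ml 12.5% carbohydrate", also in the resuscitation room.

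The readiness check (Steward score and wakefulness grade) is introduced for the drinking arms only: "To evaluate the resuscitation room of patients in the early feeding group". These patients first take a 30 ml test amount, are watched for abnormal swallowing, and then drink the rest. No discharge time from the resuscitation room is given for them. The nearest time limit, in item 3 of the drinking evaluation, is that "the dose was completed within 2 hours after the operation".

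Among the secondary endpoints, section 1.2.2.1 lists "The incidence of hypoxemia and reflux aspiration within 24h after surgery". Hypoxemia is an SpO2 below 91% on air, and reflux aspiration is vomiting with severe coughing followed by hypoxemia and lung rales. The same list scores thirst and hunger at 2, 6 and 8 h after surgery, but gives no reading times for SpO2 or for nausea and vomiting.

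Section 1.2.2.2 starts the general adverse-event window at the start of oral carbohydrates. It starts the nausea, vomiting, hypoxemia and antiemetic windows at the first drug administration.

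**The concern.** A threshold reading such as SpO2 below 91% is found only when SpO2 is being read. If one arm goes to the ward at 30 min and the others stay in recovery under observation until they have drunk, the same true desaturation rate can produce more recorded events in the drinking arms. The comparison with Group C would then mix surveillance with risk, and no later analysis could separate them, because readings never taken cannot be recovered.

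Safety is a stated aim, "To evaluate the effect of early oral carbohydrate administration on the comfort and safety of patients undergoing unilateral knee arthroplasty", and section 2 expects no increase in adverse events. An excess in the drinking arms that came from closer watching would be a false signal against early drinking.

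The windows in section 1.2.2.2 add to the problem. They open at an intake that Group C does not have. For general adverse events, the postoperative carbohydrate that opens the window is given to only one of the three arms.

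**Working it through.** The plan states no event rate, PACU stay or detection figure, so there is no figure to reproduce. The check sets the sections side by side and then bounds the effect under stated assumptions.

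**Side by side**

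| Item | Group C | EOF 1 and EOF 2 |
|---|---|---|
| Vital-sign observation in recovery | 30 min, then ward | No duration stated |
| Readiness assessment | Not described | Steward score and wakefulness grade |
| Observed drinking step | None | 30 ml, swallowing watched, then the rest |
| Time limit | None beyond the 30 min | Drink finished by 2 h after the operation |
| Ward monitoring of SpO2 or vomiting | Not described | Not described |
| Window for hypoxemia and aspiration (1.2.2.1) | 24 h after surgery | 24 h after surgery |
| Start of windows in 1.2.2.2 | No postoperative study intake | Study drink (carbohydrate in EOF 2 only) |

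The length of the 24 h window does not differ by arm. What may differ is how intensively the early part of it is observed.

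**Possible difference in PACU time**

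- Group C stay: 30 min (section 3.1.2).
- EOF stay: not stated. Assumed to be 30 to 120 min. The upper end borrows the limit for finishing the drink and takes arrival as the end of surgery.
- Excess: 0 to 120 − 30 = 90 min.
- Share of the 24 h window (1440 min): 0% to 90/1440 = 6.25%.

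**Illustrative ratio of recorded events**

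Assume equal true event rates in all arms, constant over 24 h, with full detection in the PACU and detection fraction d on the ward. With T the PACU stay in minutes:

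ratio = [T_EOF + d × (1440 − T_EOF)] / [T_C + d × (1440 − T_C)]

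With T_C = 30 and an assumed d = 0.5:

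- T_EOF = 120: (120 + 0.5 × 1320) / (30 + 0.5 × 1410) = 780/735 = 1.06.
- T_EOF = 30: 735/735 = 1.0.

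With d = 1 the ratio is 1.0 whatever the stay. If events cluster early, the ratio exceeds 1.06 for the same stay and detection fraction. The documents give no event timing, so that increase cannot be estimated.

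**The case against.** A reader might infer that the drinking arms are watched for up to four times as long and that the safety comparison is therefore biased. The documents do not support this.

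- **Length of stay.** The 2 h limit concerns finishing the drink; it is not a stay in recovery. All patients have spinal anesthesia, and one who meets the criteria early could drink and leave within 30 min.
- **Detection on the ward.** Ward monitoring is described for no arm, so poorer detection there is an assumption. The 2, 6 and 8 h thirst and hunger scores imply planned contact in every arm. Vomiting, and aspiration as defined, are largely overt events. The detection argument bears mainly on brief, silent desaturation.
- **Size.** A ratio of 120/30 = 4 needs a 120 min stay and no detection at all on the ward. A ratio of 120/(30 + 0.5 × 90) = 1.6 counts only the first 120 min of a 1440 min endpoint.
- **Events before the drink.** One might also think that a window opening at surgery counts desaturations before the drink against the drinking arms. It does not: such events are counted in all three randomised arms alike.
- **Reach.** More detection in the drinking arms would work against the expected finding of no increase, so it would not produce a false claim of safety. The primary endpoint is a laboratory index on day 1, and EOF 1 and EOF 2 share the same recovery-room procedure, so neither is touched.

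All of this stands and limits the point. It does not remove the lack of arm-independent reading times. That is a data-collection matter which an analysis plan cannot repair afterwards.

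On the windows in section 1.2.2.2, one could say that every patient has a sugary drink 2–3 h before surgery and that this might serve as a common start. The text does not say so, and it does not define what drug administration means in Group C.

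**Conclusion.** The point holds as a possibility of differential ascertainment, not as a demonstrated bias. The protocol fixes the recovery-room observation time for Group C only, adds assessment and observed drinking of open-ended duration in the other two arms, and sets no common times for SpO2 or for nausea and vomiting. If detection is closer in the drinking arms, their recorded hypoxemia and vomiting would be raised relative to Group C.

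The size cannot be computed from the documents. It is zero if stays or detection are equal. It is about 1.06 over 24 h under three assumptions taken together: a 120 min stay in the drinking arms, half detection on the ward, and a constant event rate.

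The undefined start for Group C in the section 1.2.2.2 windows is the firmer defect, since it can be read directly from the text. Both matter for the secondary safety comparison with Group C only, and both are cheap to correct.

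**What to change.** 1. In all three arms, record SpO2 on air and nausea/vomiting at the same times measured from the end of surgery: for example 30 min, the existing 2, 6 and 8 h time points, and 24 h.
2. Base the between-arm comparison with Group C on these common readings, and report the 24 h incidence of all recorded events alongside.
3. Start the adverse-event and antiemetic windows of section 1.2.2.2 at the end of surgery in every arm, replacing the start of oral carbohydrates or of drug administration.
4. Record the clock time of each event for description only. Do not exclude events before the drink, because Group C has no matching first sip and the exclusion would make the arms unequal.

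The cost is a few extra bedside readings per patient, mostly at contacts that already exist. The change concerns measurement and counting only; the feeding regimen and clinical care stay as they are.

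### The Steward limb item is scored 1–3 while the other two items are scored 0–2, so a patient who does not cough on command can still reach the drinking threshold of 6

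*Protocol*

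**What the plan says.** Section 3.1.2 of the protocol (management within the PACU) allows a patient in EOF 1 or EOF 2 to drink when two conditions are met: a Steward score of 6 and wakefulness grade 3. The list headed as the evaluation of the drinking index then defines both scales.

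- Steward, wakefulness: "awake: 0-no response to stimulus; 1-some response to stimulus; 2-full awake". This runs 0–2.
- Steward, airway: 0 means that support is needed. Levels 1 and 2 are given as "respiratory tract can maintain patency without support; 2-patient can cough according to the" doctor's instruction. This also runs 0–2, and cough on command is the top level.
- Steward, limb movement: "Body mobility: 1 point-the patient has no body activity; 2 points-the unconscious activity of the" limb, and then 3 points for conscious movement. This runs 1–3.
- Wakefulness grade 3 builds on grade 2, where the patient "At the same time can also open the mouth, stretch the tongue". At grade 3, "they can also clearly tell their own name, age and other information".

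The protocol gives no total range for the Steward score, no minimum per item and no separate cough requirement. Drinking starts with a 30 ml trial: "After observing no abnormal swallowing, the patient was instructed to drink the remaining drinks as needed".

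**The concern.** On two items the worst state earns 0. On the limb item, a patient who does not move at all earns 1. That point enters every total, so a threshold of 6 sits one below the printed maximum and one missing level elsewhere can be made up by it. The level that matters most before oral fluid is given is cough on command, and the airway item is the only place where the protocol asks for it.

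The threshold decides when patients in both early-feeding arms may drink. Safety is part of the secondary objective (section 1.1.2), and hypoxaemia and reflux aspiration within 24 hours are listed endpoints (section 1.2.2.1). Staff who score the limb item as printed and staff who score it 0–2 would also clear different patients at the same nominal 6.

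**Working it through.** **Inputs** (all from section 3.1.2): wakefulness W ∈ {0, 1, 2}; airway A ∈ {0, 1, 2}, where A = 2 is cough on command; limb movement L ∈ {1, 2, 3}; threshold 6 together with grade 3. The protocol states no total or maximum, so there is no stated sum to reproduce.

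**Step 1: range as printed.** Total = W + A + L. The minimum is 0 + 0 + 1 = 1 and the maximum is 2 + 2 + 3 = 7. There are 3 × 3 × 3 = 27 combinations.

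**Step 2: combinations (W, A, L) that reach the threshold.**

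| Combination | Total | Coughs on command? |
|---|---|---|
| (1, 2, 3) | 6 | yes |
| (2, 1, 3) | 6 | no |
| (2, 2, 2) | 6 | yes |
| (2, 2, 3) | 7 | yes |

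Four of 27 combinations total 6 or more. One of them, (2, 1, 3), lacks cough.

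**Step 3: add the grade 3 condition.** Grade 3 covers mouth opening, tongue protrusion and stating one's name and age. It says nothing about cough, so it does not remove (2, 1, 3). If grade 3 is taken to imply W = 2 and L = 3, the combinations left are (2, 1, 3) and (2, 2, 3), which is 2. If it is taken to imply only W = 2, then (2, 2, 2) stays as well, which is 3. The no-cough combination passes in both cases.

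**Step 4: the comparator.** The threshold appears in the available text as a bare number. A sign may have been lost when the PDF was read, so its absence is not counted against the plan. The possible readings are:

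- At least 6: the no-cough patient passes (Step 2).
- Exactly 6: the no-cough patient passes, and the fully recovered patient, at 7, does not match.
- More than 6: only (2, 2, 3) = 7 passes, and cough is then required.

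**Step 5: rescore the limb item 0–2.** The total runs from 0 to 2 + 2 + 2 = 6. Only (2, 2, 2) reaches 6. The no-cough patient becomes (2, 1, 2) = 5 and fails.

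**Step 6: the alternative repair.** Keep the printed 1–7 scale and require a total of at least 6, A = 2 and grade 3. (2, 1, 3) is removed and (2, 2, 3) passes; (2, 2, 2) also passes if grade 3 does not imply L = 3.

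These are counts of score patterns. They say nothing about how many patients show each pattern.

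**The case against.** The case for leaving this alone has four parts.

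1. *No stated sum is wrong.* The protocol never says that 6 is the full score, and a threshold one point below the maximum is a legitimate choice. It is true that the intended maximum is inferred from the 0–2 scoring of the other two items. The uneven numbering is nevertheless on the page, and nothing shows that a lower threshold was chosen on purpose. The point is best described as an inconsistent scale definition.

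2. *A lost greater-than sign would remove the problem.* On the printed scale, more than 6 means 7, and cough would be required. This reading is unlikely. Less-than signs survive in the hypoxaemia definition (section 1.2.2.1) and the transfusion threshold (section 3.1.2). The signs that seem to be missing from the pain-score thresholds in section 3.1.2 look like at-most and at-least signs. At least 6 is therefore the more plausible reading.

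3. *The count of two passing combinations rests on an assumption.* The grade definitions do not say that grade 3 implies conscious limb movement. This stands, and the count is therefore given as 2 or 3. The main result does not depend on it.

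4. *The patient at issue is probably rare and is otherwise protected.* Such a patient is fully awake, keeps the airway open, moves purposefully and states name and age, yet does not cough when asked. "All patients underwent lumbar anesthesia", a test swallow comes first, and abnormal swallowing and gastro-oesophageal reflux are exclusions (section 4.2). This stands and is why the point is minor. The swallowing checks do not test cough, however, and the documents give no frequency for the pattern.

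**Conclusion.** The concern holds, as a minor point. As printed, the Steward total runs 1–7, and a fully awake patient who does not cough on command scores 6 and meets the drinking threshold. This is so whether the threshold means exactly 6 or at least 6; it fails only if more than 6 was meant, which is unlikely. No other condition in the protocol requires cough. That 6 was meant as the full score is an inference.

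The practical risk is small, and no safety failure has been shown. The rule is the same in EOF 1 and EOF 2, so it does not bias the comparison between them. No effect on the day 1 insulin resistance endpoint or on the error rate has been shown.

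**What to change.** In section 3.1.2, score the limb item 0 for no movement, 1 for unconscious movement and 2 for conscious movement. The maximum is then 6, and a score of 6 requires the best level on every item.

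If a lower threshold is intended, keep the 1–7 scale, state its range, write the threshold with its comparator, and add that the airway item must equal 2.

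Either change takes about one line. A few patients might drink slightly later, still inside the limit by which "the dose was completed within 2 hours after the operation". That is a judgement, since the documents give no figures on it.

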#### 4. Subject recruitment and protective measures

##### 4.1 Inclusion criteria

- Age 18-79 years;
- Patients undergoing unilateral total knee arthroplasty or unicondylar joint replacement;
- Normal diet;
- ASA grade I~III;
- BMI 18-30 kg / m^2;
- No intraspinal anesthesia contraindications.

##### 4.2 Exclusion criteria:

- Preoperative existence of gastric emptying disorders, such as gastrointestinal obstruction, gastroesophageal reflux, or previous gastrointestinal surgery;
- Patients with diabetes mellitus, severe renal dysfunction, or other severe metabolic diseases;
- History of motion sickness;
- Mental disorder, alcoholism, or a history of substance abuse;
- Patients with abnormal swallowing function;
- The operation time is greater than 3 hours;
- Maltodextrin fructose allergy or intolerance;

4.2 Standards for dropout cases: signed the informed consent form and screened the Protocol version: May 17, 2023

qualified withdrawal cases in the pre-intervention, during the intervention and after the intervention follow-up process after entering the study.

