#### 4.3 Case exclusion criteria:

- Signed the informed consent, entered the study but was found not to meet the inclusion criteria during the project supervision or after the completion of the study;
- Did not sign the informed consent;
- The intervention was not performed according to the treatment standards and had poor compliance;
- Failed to accept the intervention, did not comply with or assume the corresponding responsibilities and obligations of the informed agreement.

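### The 3-hour operation-time exclusion cannot be checked at pre-surgery screening and the time of randomisation is not fixed; separately, a readiness check confined to the early-feeding arms, read with section 4.3, could bias comparisons with group C

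*Protocol*

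**What the plan says.** **Eligibility and its timing.** Section 3.1.1 of the protocol enrols patients who "met all enrollment criteria and did not meet any of the exclusion criteria". Section 3.1.2 places this before the operation: "Eligible patients were screened before surgery, and an informed consent form was signed". One of the exclusion criteria in section 4.2 is "The operation time is greater than 3 hours". It is worded as the actual time, not the planned or expected time.

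**Randomisation.** Section 3.1.2 continues: "Patients enrolled in the experiment were randomly assigned into one of the three groups". No time point relative to surgery is given. The sentence follows preoperative screening and consent, but the paragraph stands under the line "Management within the PACU".

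**Recovery room.** The Steward and wakefulness assessment is introduced with "To evaluate the resuscitation room of patients in the early feeding group". The first-sip swallowing observation and the 2-hour window for finishing the drink also concern only the groups that drink. For control the text is "Group C patients observed 30min vital signs, returned to the ward to fast and drink for at least 6 h", with no score. The protocol does not say what happens to a patient who does not pass the assessment.

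**Removal of cases.** Section 4.3 excludes cases in which the intervention was not carried out to the treatment standards with poor compliance, and cases that "Failed to accept the intervention" or did not meet the obligations of the consent agreement. It also excludes patients later found ineligible, but names only the inclusion criteria. It does not mention operation time.

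**The concern.** There are two separate problems.

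First, a criterion that must be satisfied at enrolment cannot be known at enrolment. What follows depends on when patients are randomised, and the protocol leaves that open. If allocation precedes surgery, someone must decide after allocation whether a patient with a long operation stays. Section 4.3 gives no clear answer, because its late-ineligibility rule does not cover exclusion criteria.

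Second, a check defined by arm can only be applied once the arm is known, so it comes after allocation on either reading of the timing. A patient in EOF 1 or EOF 2 who is slow to recover, or too unwell to want the drink, may end up not receiving the intervention as described and so come within the wording of section 4.3. A comparable patient in group C has no such hurdle. If the early-feeding patients are then removed, those arms become a selected subset while group C does not. Section 1.2.2.1 lists nausea and vomiting, hypoxemia and reflux aspiration as endpoints, and early recovery state could plausibly relate to these.

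**Working it through.** The document gives no sample size, SD, share of operations over 3 hours or share failing the readiness check. There is therefore no figure to reproduce, and every numerical input below is an assumption.

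**Step 1. Can the criterion be applied when required?** Required: no exclusion criterion met at screening (section 3.1.1), before surgery (section 3.1.2). Criterion: actual duration over 3 hours (section 4.2), known only once surgery has run that long. The two cannot both be followed as written.

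**Step 2. What does the 3-hour rule do to the comparison?**
- Allocation in the PACU after surgery: duration is already known, so no randomised patient is lost to this rule.
- Allocation before surgery: a share q is removed. The rule is the same in all three arms and is settled before the recovery-room intervention, so the expected loss is q in each arm and the expected difference between arms is zero.
- Precision cost: the confidence interval widens by the factor 1/√(1 − q). For q = 5%, 1/√0.95 = 1.026; for q = 10%, 1/√0.90 = 1.054. That is 2.6% to 5.4%.

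**Step 3. What could the readiness check plus section 4.3 do?** Let a share f of an early-feeding arm be removed and none of group C. Let removed patients be d SD worse than retained ones, with no treatment effect. If retained patients have mean m, the whole arm has mean m + f·d, and so does the intact group C. The early-feeding arm after removal has mean m. The spurious difference is therefore f·d SD.

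| f removed | d = 0.25 | d = 0.5 | d = 0.8 |
|---|---|---|---|
| 2% | 0.005 | 0.010 | 0.016 |
| 5% | 0.0125 | 0.025 | 0.040 |
| 10% | 0.025 | 0.050 | 0.080 |
| 20% | 0.050 | 0.100 | 0.160 |

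**Step 4. What would such a shift do to a two-sided 5% test?** With n analysed per arm, the standard error of a difference in means is √(2/n) SD: 0.200 for n = 50 and 0.141 for n = 100. For a shift b, the false-positive rate is 1 − Φ(1.96 − b/SE) + Φ(−1.96 − b/SE).

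| Shift b (SD) | n = 50 per arm | n = 100 per arm |
|---|---|---|
| 0.005 | 5.0% | 5.0% |
| 0.025 | 5.2% | 5.4% |
| 0.05 | 5.7% | 6.4% |
| 0.10 | 7.9% | 10.9% |
| 0.16 | 12.6% | 20.5% |

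**Step 5. Which comparisons are exposed?** EOF 1 and EOF 2 face the same check, so this mechanism creates no expected bias between them. Only EOF 1 versus C and EOF 2 versus C are exposed.

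**The case against.** A reader might infer that randomised patients are certainly lost after allocation, and unequally by arm. The documents do not support that.

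- **Timing.** The allocation paragraph sits under the PACU heading. If patients are randomised there, the 3-hour rule costs no randomised patient, and late allocation may already be intended. This stands: the defect is that the time is not stated, not that it is shown to be wrong.
- **The 3-hour rule as a source of imbalance.** It applies alike to all arms and precedes the intervention. It cannot be expected to unbalance them. This stands.
- **Removal for failing the check.** Section 3.1.2 attaches no consequence to failing, and the 2-hour window leaves room to wait and reassess. In context, the section 4.3 wording reads most naturally as refusal or non-compliance by the participant, not staff withholding a drink. All patients have lumbar anaesthesia, so the share failing may be small. Section 4.3 also covers group C, where a patient who breaks the fast could be removed. These points make unequal removal a possibility, not a stated rule. They do not dispose of it: the wording is broad enough to catch an undelivered drink, and removal from group C for breaking the fast is a different selection that need not cancel the first.
- **Size and direction.** Nothing in the document shows that slow-recovering patients have worse day-1 insulin resistance. The direction is assumed along with the size. This stands.
- **Analysis sets belong in the SAP.** Often so, and an SAP not seen here may define them. But eligibility, time of allocation and removal of cases are matters this protocol itself sets out, and section 4.3 as written permits removal on compliance.

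**Conclusion.** The point holds in two limited parts.

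From the text alone: the operation-time exclusion conflicts with pre-surgery screening, and the time of randomisation is not fixed. At worst this costs precision, equally in expectation across arms.

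Conditionally: if patients who do not pass the early-feeding readiness check, or do not take the drink, are removed under section 4.3, the comparisons of EOF 1 and EOF 2 with group C could be biased. The carbohydrate-versus-water comparison is not affected by this route. The size cannot be derived from the document. The range of about 0.005 to 0.16 SD assumes 2% to 20% removed from an early-feeding arm, none from group C, and removed patients 0.25 to 0.8 SD worse. At the low end this is negligible; at the high end it would matter. The sponsor should correct the wording, because the correction is cheap and settles both parts.

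**What to change.** 1. State when allocation is opened. The cleanest choice is in the PACU after surgery has ended, with preoperative consent kept and the operation-time criterion applied before allocation. If allocation is to be before surgery, reword the criterion as expected operation time.
2. Apply the protocol's own existing readiness assessment alike to all consenting patients before allocation. If it stays after allocation, state that not passing it is no reason for removal.
3. Replace the compliance-based removals in section 4.3 with a rule that every randomised patient is kept in the allocated arm for the primary analysis. Use a per-protocol set as a sensitivity analysis only.

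No clinical threshold in the protocol needs to change for this. The costs are changes of wording, opening the allocation in the PACU, a brief assessment in patients who go on to group C, and some consented patients who are never randomised. Randomising only patients who pass the assessment would also restrict the trial population to them, which should be stated.
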